7.3. Enrollment

Once informed consent is obtained and the patient is enrolled, the coordinator will double-check previous history of porphyria, allergies, and hypersensitivity to the potential ASM listed in the study to provide a list of the treatment protocols that could be used for the patient if allocated to intervention. On the same day, the study coordinator will schedule the rs-fMRI for the following days and inform the research and the care teams of the scheduled date. This date should be within three days at maximum, and the intervention allocation must be done within six days from enrollment. Considering those dates, the minimum and maximum times from MSABI to the first rs-fMRI are 4, and 48 days correspondingly. The minimum and maximum times from MSABI to the intervention are 5 and 51 days, correspondingly. The family will be told that all the rs-fMRI results will be provided and explained after the follow-up research tests, and no further instructions are needed.

Screening/enrollment interview Activities (Day 0)

- BIS assessment for score (>80) through interview with potential LAR.
- Written Informed Consent Obtained from LAR.

- Consent must be obtained within 90 days from the participant's MSABI.
- Confirming baseline variables are collected through medical chart review.
 - Supratentorial decompressive craniectomy, current GCS score, presence of spontaneous ventilation.
- Verify with the LAR about: porphyria, co-morbidities, medical implants or contraindications for MRI, allergies, and hypersensitivity to the potential ASM.
- Provide a list of the treatment ASMs recommended for this participant that could be used if allocated to intervention.
- Notify Clinical Team about participant enrollment.
 - Verify with study team about which 2 combined ASMs could be administered in case of allocation to treatment.
 1. Phenobarbital 20 mg/kg loading dose
 2. Levetiracetam 60mg/kg loading dose
 3. Lacosamide 10 mg/kg loading dose
 4. Valproate 30 mg/kg loading dose
 5. Fosphenyton 20 mg/kg loading dose

7.4. Study Visits

This study is designed for in-hospital patients; no additional research team visits are planned. Clinical information after enrollment will be collected from medical charts (Glasgow coma score at the rs-fMRI#2 day), and the last data collection date at the outpatient clinic will be collected from medical records from the subjects that were discharged alive on ASM and scheduled to follow-up by one of the NSICU Post-Discharge clinics. That visit is described under the next final visit section No. 7.5. For details about the in-hospital research activities visit Treatment Design section No. 6.

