Interventions	
Participants that are SzNET positive will receive a loading ASM combination dose of Levetiracetam (60mg/kg) and Phenobarbital (20 mg/kg), followed by maintenance dosing for weight and age of both medications from three to ten days until the repeat rs-fMRI.
 
If care team considers either of those medications cannot be used, then they are allowed to administer any other combination of two ASM from the following list as the loading dose:
 
 1. Phenobarbital 20 mg/kg 2. Levetiracetam 60mg/kg 3. Lacosamide 10 mg/kg 4. Valproate 30 mg/kg 5. Fosphenytoin 20 mg/kg 
Maintenance dose: Standard dosing for weight and age of both medications used for the loading dose from three to ten days until the repeat rs-fMRI.
 
Participants with GCS 9 to 12 will not be assigned phenobarbital as one of the intervention ASM and the loading dose of one of the two ASM selected will be omitted. In this case the ASM list doses remain the same, and the recommended intervention will be Levetiracetam with loading and maintenance doses and lacosamide only maintenance doses.
 
For all participants, the protocol driven ASM can be continued, suspended or modified by the care team after the repeat rs-fMRI is obtained. ASM administration after the follow up scan is not considered part of the protocol intervention. Step-wise withdrawal is encouraged in case the care team decides to suspend the ASM given as part of the protocol.

Outcome Measures	
Definitions are provided in the abbreviations table.
 
Aim 1. Pre and Post treatment SzNET activity Aim 1a. Pre and post-treatment SzNET total volume medians Aim 1b. Pre and post-treatment SzNET power spectrum medians
 
Aim 2. Presence of SzNET in rs-fMRI #1 (binary)
 
Aim 3. Follow-up EEG improvement (binary).

	
Aim 4. Connectivity improvement of typical RSN in MSABI patients after intervention (Binary).
 
Aim 5. Follow up outcomes (3 months from hospital discharge) collected from one of the NSICU Post-Discharge Clinics, include: NDDI-E, PROMIS emot. Dist. -Anxiety - Short form, Liverpool Adverse Events Profile questionnaire, QOLIE-10-P and MoCA
 
Aim 6.
 
Aim 6a. Enrollment rate.
 
Aim 6b. Dropout rate.

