Investigate association between post-intervention EEG improvement and SzNET response. The estimand of interest is the relative risk of EEG improvement in patients with more than 50% improvement of their SzNET by TVR and PSI.

3.4. Aim 4

Investigate the association between the post-intervention typical resting state networks (RSN) connectivity improvement and the SzNET response. The estimand of interest is the relative risk of improvement of the RSNs in the patients with more than 50% of improvement of their SzNET by TVR and PSI.

3.5. Aim 5

Describe psychosocial functional measure outcomes and ambulatory ASM toxicity at 3 months from hospital discharge. The estimates of interest will be the PROMIS Emotional Distress—Anxiety— Short Form, the Neurological Disorders Depression Inventory for Epilepsy (NNDI-E), the QOLIE-10-P, the Telephonic Montreal Cognitive Assessment, and the Liverpool adverse event profile test. All will be assessed at the 3 month follow up visit by one of the NSICU Post-Discharge clinics. This aim only applies to the patients that are discharged alive from the hospital and will include results from visits until 14 months after the enrollment start.

3.6. Aim 6

Assess the trial's design feasibility success in enrollment and retention for our actual institutional context by evaluating the enrollment rate and dropout rate among participants at the end of the trial. It will be composed by two sub aims.

Aim 6a

Measure the participants enrollment rate during the hole study enrolling months. The estimand of interest will be the rate of enrolled patients per month.

Aim 6b

Measure the participants dropout rate among participants. The estimand of interest will be the dropout rate from the total enrolled participants at the end of the study.

4. Study Design

This is a prospective interventional, uncontrolled, open-label, single center pilot study in moderate to severe acute brain injury (MSABI) patients with suppression of consciousness. The study main outcomes require pre and post-intervention rs-fMRI data collection to characterize the evolution of SzNET, a physiological measure of brain function. Clinical implementation of rs-fMRI is still novel, not frequently performed at early stages of MSABI, and has few medical indications as a follow-up test. As this data is infrequently generated during the standard of care (SOC), a prospective interventional study with an ASM intervention and a research funded rs-fMRIs is needed.

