The target population is in the UNC intensive care unit, and to prioritize the human subjects' wellbeing, the patients will receive their standard clinical monitoring and therapy per the local care team, including EEG, antiseizure therapy, and head imaging as clinically indicated. Once stable for MRI, subjects will receive the study-related rs-fMRI #1. If SzNET are detected (SzNET+), the subject will start the study treatment protocol, followed by post-treatment repeat rs-fMRI (rs-fMRI#2) and EEG. Those patients negative for SzNET in the rs-fMRI#1 (SzNET-) will not

have intervention or research follow up EEG and rs-fMRI, but if they are followed by one of the NSICU Post-Discharge clinics, the information obtained from their assessments will be collected as part of this study.

Rationale for intervention with ASM

The purpose of this study is to test the correlation of SzNET in MSABI with epileptogenic activity. To benchmark this correlation, we will compare the response of SzNET to ASM with well-known effect in the epileptogenic activity. Previous data in epilepsy shows that SzNET improvement is related to clinical improvement¹³, and those clinical effect sizes of seizure improvement have been measured for multiple pharmacological treatments including the ones listed for this protocol intervention^{26,27}. We hypothesize that SzNET improvement will be similar to the effect size expected for the selected ASM. If we are correct, SzNET could help predict clinical outcomes related to epileptogenic activity. To achieve this, we need treatment protocols with proven consistent clinical response and a large effect size. The recommended protocol for a effective response is a combination of intravenous phenobarbital and levetiracetam at loading doses²⁶. However, since the main outcome measures are quantitative and smaller effect size responses could still be detected, for this pilot trial we allow a list of alternative ASM protocols with anticipated similar efficacy. The purpose of this alternative options is that the care team can use a different protocol if it is more appropriate given the patient's particular characteristics.

Rationale for stratification by EEG

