4.2. Experimental Design

This pilot study is a stratified interventional study that will evaluate the response of an exploratory biomarker. There will be no placebo-controlled groups, and the study main intervention will be systematically assigned to all subjects with SzNET identified by the first rs-fMRI. Patients without SzNET will not receive the study treatment and will continue their medical therapy as directed by their care team. They will be included in the required analysis for aim 2 and 5. Two specialists will assess the two post-intervention follow-up studies, the rs-fMRI#2 and the repeat EEG, providing the only blinding needed. These study design elements will ensure the technical requirements necessary to calculate the sample size required for a larger trial in EEG-negative patients with SzNET-positive and explore two important aspects of the biomarker SzNET: its correlation with the EEG response of patients and the effect size of its response to the intervention ASM.

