7.5. Final Visit

3 Months Post Day of Hospital Discharge

- Patients who are discharged will be seen in one of the NSICU Post-Discharge clinics.
- The visits are scheduled at 3 months after hospital discharge.
- This visit is not scheduled by the research staff, and its information will only be obtained through medical chart review.
- The scales that are performed in patients that are seen in one of the NSICU Post-Discharge clinics will evaluate functional, cognitive, and behavioral/psychiatric outcomes:
 - ASM toxicity: Liverpool adverse event profile test (LAEP) – If the patient is on ASM^{36,37}
 - Cognitive outcome: Telephonic Montreal Cognitive Assessment (T-MoCA- 5mins protocol)³⁸
 - Anxiety: PROMIS Emotional Distress—Anxiety— Short Form³⁹
 - Depression: Neurological Disorders Depression Inventory for Epilepsy (NNDI-E)⁴⁰
 - Quality of Life: QOLIE-10-P⁴¹

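### Section 7.4 limits the 3-month clinic data to patients discharged on ASM, while sections 3.5, 4, 4.2, 6 and 7.5 set no such condition for Aim 5

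*Combined protocol and SAP*

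**What the plan says.** The combined protocol and SAP define who supplies the 3-month data in several places.

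- **Section 7.4 (Study Visits):** the outpatient data come from subjects "discharged alive on ASM and scheduled to follow-up by one of the NSICU Post-Discharge clinics". This sets three conditions: alive at discharge, on ASM at discharge, and booked at a clinic.
- **Section 3.5 (Aim 5):** "This aim only applies to the patients that are discharged alive from the hospital". ASM is not mentioned. The same section adds a time limit: the aim "will include results from visits until 14 months after the enrollment start".
- **Section 4 (Study Design):** for SzNET- patients followed at one of the clinics, "the information obtained from their assessments will be collected as part of this study".
- **Section 4.2 (Experimental Design):** of patients without SzNET, who receive no study treatment, "They will be included in the required analysis for aim 2 and 5".
- **Section 6 (SzNET stratification):** for SzNET- patients, the only condition for the 3-month follow-up is a clinic booking.
- **Section 7.5 (Final Visit):** five scales are listed, and only the Liverpool toxicity scale carries the condition "If the patient is on ASM".
- **Section 1 (Synopsis, Interventions):** after the repeat scan the care team may continue, change or stop the ASM, and "Step-wise withdrawal is encouraged in case the care team decides to suspend the ASM given as part of the protocol". The protocol therefore foresees that some treated patients may leave hospital off ASM.

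**The concern.** Section 7.4 sets a narrower population than the sections that define the aim and its analysis. A chart abstractor who follows 7.4 and one who follows 3.5 would build different Aim 5 datasets, and the denominator of every Aim 5 summary would depend on which section was used.

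The ASM condition makes sense for a drug-toxicity scale. It does not make sense for anxiety, depression, cognition or quality of life. With 7.4 as the filter, those four outcomes would be summarised in patients selected by a treatment decision, and ASM use at discharge may well be related to the outcomes themselves.

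The filter could also fall unevenly on the two SzNET groups, because the SzNET- patients receive no study ASM. Section 2.2 says the pilot should test whether outcomes and trends in relation to SzNET can be collected through the clinics. An uneven filter would weaken that description.

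**Working it through.** **1. The plan's own counts.** Section 5.1 aims for 11 SzNET+ patients per EEG stratum and expects SzNET in 30% of EEG- and 67% of EEG+ patients.

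- EEG-: 11 / 0.30 = 36.7, rounded up to 37.
- EEG+: 11 / 0.67 = 16.4, rounded up to 17.
- Total: 37 + 17 = 54, which matches the stated enrolment.
- SzNET-: 54 − 22 = 32, which matches the number in section 6. As a share, 32 / 54 = 59%.

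No expected number is stated for Aim 5 itself.

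**2. The conditions side by side.**

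| Section | Alive at discharge | Clinic follow-up | On ASM |
|---|---|---|---|
| 3.5 | yes | visit at a clinic | no |
| 4 (SzNET-) | not stated | yes | no |
| 4.2 (SzNET-) | not stated | not stated | no |
| 6 (SzNET-) | not stated | yes | no |
| 7.5 | discharged | yes | Liverpool scale only |
| 7.4 | yes | yes | **yes, for all data** |

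Only 7.4 applies the ASM condition to everything. If every contributor had to be discharged on ASM, the separate condition on the Liverpool scale in 7.5 would be largely redundant. It would matter only for patients who stopped between discharge and the visit. The two conditions also refer to different times: 7.4 looks at discharge, whereas 7.5 looks at the visit.

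**3. How many patients could be lost.** The number dropped by 7.4 is the number of clinic attenders who were off ASM at discharge. The documents give neither survival to discharge, clinic attendance nor the share off ASM. For the SzNET- group the bound is

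lost = 32 × (share alive and attending) × (share off ASM at discharge).

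Taking the first share as 1, which is the most extreme assumption, gives 0 lost if none are off ASM, 16 if half are, and 32 if all are. Lower survival or attendance shrinks these figures in proportion. Treated patients whose ASM was stopped after rs-fMRI #2 would add to the loss, out of at most 22.

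**4. The month-14 limit, checked separately.** Enrolment lasts 12 months (synopsis), and "The visits are scheduled at 3 months after hospital discharge" (section 7.5).

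- Last discharge that can contribute: 14 − 3 = month 11.
- Earliest visit for a patient enrolled at month 12: 12 + 3 = month 15, which is after month 14.
- Under uniform accrual over 12 months (assumption), the share of enrollees whose visit can fall by month 14 is (14 − 3 − stay) / 12, where stay is the time from enrolment to discharge. This is 91.7% for zero stay, 83.3% for 1 month, 75.0% for 2 months and 66.7% for 3 months, before deaths and non-attendance.

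This limit does lose late and long-stay patients, but it contradicts no other rule in the plan.

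**The case against.** The best defence is that 7.4 is an isolated slip. Sections 3.5, 4, 4.2, 6 and 7.5 carry no general ASM condition, and neither does the Aim 5 plan in section 8.3. The Table of Events shows the 3-month questionnaires without the asterisk that marks SzNET+ activities, and 7.4 itself refers the reader to 7.5 for the visit. Staff may therefore collect the data correctly whatever 7.4 says. This makes the loss possible rather than certain. It does not remove the contradiction, because 7.4 is the section that states where the outpatient data come from.

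The size is also uncertain. SzNET- patients are untreated only by the protocol. Section 4 leaves them on standard care, including antiseizure therapy where indicated, and section 2.1 calls empirical ASM widely accepted. A reader might infer that 7.4 removes most of the SzNET- group; the documents do not support that. Nor does the synopsis wording on step-wise withdrawal show that stopping is common.

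Aim 5 is also exploratory, limited to summary statistics and without a hypothesis. Finally, removing the condition would not yield data on all survivors: section 7.5 says the research staff do not schedule the visit and only read the chart, so the sample remains one of clinic attenders. These points stand. They limit the harm and shape the fix.

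**Conclusion.** The contradiction is real and minor. Section 7.4 must be reconciled with 3.5, 4, 4.2, 6 and 7.5. Followed as written, it would select the Aim 5 sample on ASM use at discharge and drop an unknown number of clinic attenders, possibly none. Any figure rests on survival, attendance and ASM-at-discharge rates that the documents do not give. No power, error rate or primary result changes.

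A reader might go further and infer that the month-14 limit is a second conflicting rule, or that it should move to month 16 because the study lasts 16 months. The documents do not support either reading. A data cut before study end is consistent with a 16-month study. The amendment summary shows that the limit was set on purpose, to keep the study length fixed when time to discharge is unpredictable. Section 8.1 requires rescoring by separate staff and double data entry, and the plan does not say whether the 16 months include that work. The limit is a trade-off. Its consequence, that nobody discharged after month 11 contributes if visits occur at three months, is worth stating but is not an error. The percentages above also assume uniform accrual for a full year; section 5.1 stops enrolment when the SzNET+ quotas are met, so accrual could end sooner and the loss be smaller.

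**What to change.** - Delete the ASM condition from section 7.4, so that it matches 3.5, 4, 4.2, 6 and 7.5.
- Keep the condition for the Liverpool scale only, as 7.5 already does.
- In 3.5 and 8.3, describe the Aim 5 sample as survivors seen at a post-discharge clinic, so that the summaries are not read as covering all survivors.
- Leave the month-14 limit as it is. When reporting Aim 5, state that patients discharged after month 11 could not contribute.

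The cost is a few words in the protocol and some further chart review for attenders who were off ASM at discharge. No visit, test or treatment rule changes.

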7.5. Final Visit

3 Months Post Day of Hospital Discharge

- Patients who are discharged will be seen in one of the NSICU Post-Discharge clinics.
- The visits are scheduled at 3 months after hospital discharge.
- This visit is not scheduled by the research staff, and its information will only be obtained through medical chart review.
- The scales that are performed in patients that are seen in one of the NSICU Post-Discharge clinics will evaluate functional, cognitive, and behavioral/psychiatric outcomes:
 - ASM toxicity: Liverpool adverse event profile test (LAEP) – If the patient is on ASM^{36,37}
 - Cognitive outcome: Telephonic Montreal Cognitive Assessment (T-MoCA- 5mins protocol)³⁸
 - Anxiety: PROMIS Emotional Distress—Anxiety— Short Form³⁹
 - Depression: Neurological Disorders Depression Inventory for Epilepsy (NNDI-E)⁴⁰
 - Quality of Life: QOLIE-10-P⁴¹

7.6. Phone Contacts

Not applicable.

7.7. Follow-Up Contact

The subjects will continue follow-up by their care team as appropriate, no research follow up subject visit is required beyond the 3-month from hospital discharge NSICU Post-Discharge clinic visit listed in section 7.5.

7.8. Early Discontinuations

Data to be Collected The care team may adjust the treatment plan of all patients to ensure optimal medical management, including the study intervention. Patients who do not meet the treatment criteria (which requires treatment with two of the ASM regimens specified in the protocol for at least 72h from loading dose) or who are unable to undergo the rs-fMRI#2 after completing the minimum intervention time and within 72 hours of their last dose of the intervention protocol will be considered dropouts. For these patients, only the clinical data available at the time of enrollment and their initial rs-fMRI data will be collected for analysis of aim #2. However, this data cannot be used for other outcomes analysis. Nonetheless, we will still collect information about the reason for dropping out and any reported adverse events.

Subjects missing follow-up after rs-fMRI#2 and repeat EEG are performed will have all the study data already collected except for the data asked at one of the NSICU Post-Discharge clinics for exploratory outcomes.

Criteria for Intervention Discontinuation

- Changes in the medical condition that contraindicate the use of at least two of the medications mentioned in the valid intervention list.
- Developing a medical condition that does not allow the rs-fMRI#2 scan.
- Presenting a grade 4 AE.
- Presenting a grade 2 to 3 AE without adequate measures to solve the event and prevent its study-related recurrence.

Requiring more aggressive ASM treatment because of seizures worsening or the need to change one ASM from the protocol list for another listed ASM is allowed.

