Sources of recruitment: UNCH PICU, NSICU, SICU, CTICU, CICU or MICU patients meeting study inclusion and exclusion criteria. Potential research subjects will be identified by the study team members chart screening of all the patients with EEG orders from ICU, for eligibility.

Interventional Study numbers of enrollees expected to receive the treatment regimen: Since this is a non-controlled interventional open-label pilot study, and we need a total of 20 subjects successfully to receive the study therapy AND repeat rs-fMRI, then due to intra-study attrition of 1:10, we expect to treat a total of 22 patients with the study therapy.

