8.1. Strategies that Apply to all the Aims

All statistical procedures will be performed in SAS and R. Biostatistician [name] will oversee all data analyses.

- (i) All data will be scored and rescored by separate staff members and checked for accuracy prior to double entry into our database. All datasets are backed up daily.

- (ii) Prior to statistical modeling, we will perform descriptive analyses and data visualizations to examine the distributions of all measures. Appropriate transformations to obtain approximate normality will be performed; where necessary, additional nonparametric tests will confirm results.
- (iii) Linear regression model and nonparametric tests (e.g., Wilcoxon rank sum test) will be the primary analytic tools for testing our *a priori* hypotheses. Model selection methods (e.g., Bayesian information criterion) and sensitivity analysis methods will be used to select models and assess various model assumptions. We will consider the use of appropriate covariates as detailed below in all aims.
- (iv) We will record the reasons for drop-outs, missing / censored data values, and protocol departures in the database. We will appropriately handle drop-outs and missing data (e.g., missing responses and/or covariates) by using imputation or other estimation methods (e.g., missing completely at random), while considering anticipated causes. We will carry out sensitivity analysis to evaluate different missing mechanisms.
- (v) We will use test statistics (e.g., likelihood ratio test) to test the hypotheses. To identify significant component terms in each of the models, we will examine the parameter estimates, 95% confidence intervals, and p-values of the component terms in an analysis of fixed effects for the final regression models. All statistical estimates of population parameters will be tabulated along with corresponding confidence intervals (CIs) and/or standard errors (SEs) to convey levels of precision / imprecision.

We will use graphical methods such as forest plots to visualize the analysis results. We will also include outcome-dependent exploratory analyses to generate new hypotheses.

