8.3. Aim-Specific Plans

Plans for Aim 1.

Aim 1 is to obtain preliminary data about the degree of improvement of seizure networks (SzNET) in moderate to severe acute brain injury (MSABI) patients after intervention's antiseizure medication (ASM).

Aim 1a

Measure the improvement of the SzNET total volume in MSABI patients after the intervention's ASM. The primary outcome of interest is the SzNET total volume median before and after the intervention's ASM in the target population.

H_0 : there will be no difference in the SzNET total volume median in MSABI patients before and after the intervention's ASM.

H_1 : SzNET total volume median in MSABI patients before ASM will be smaller than after the intervention's ASM.

Aim 1b

Measure the improvement of the SzNET power spectrum in MSABI patients after ASM. The outcome of interest is the SzNET power spectrum median before and after ASM in the target population.

H_0 : there will be no difference in the SzNET power spectrum median in MSABI patients before and after the intervention's ASM.

H_1 : SzNET power spectrum median in MSABI patients before ASM will be higher than after ASM.

We plan to recruit 11 patients with SzNET+EEG+ and 11 subjects with SzNET+EEG-. Therefore, 22 subjects with measurements before and after the intervention's ASM will be used in Aims 1a and 1b. We will fit linear regression models with dependent variables as follows. We calculate the changes of the SzNET total volume and the SzNET power spectrum before and after the intervention's ASM and use them as the primary dependent variables. Due to the small number of subjects, we only include an intercept to represent the mean difference before and after the intervention's ASM in the model, and we use the t-test statistic to test whether the intercept is equal to zero for Aims 1a and 1b. Moreover, we may consider demographic variables and pre-intervention EEG status (EEG+ or EEG-) if necessary.

Plans for Aim 2.

Estimate the frequency of EEG- and EEG+ patients presenting SzNET. The outcomes of interest are the proportions and differences of proportions of patients with SzNET among EEG- and EEG+ patients in this clinical setting.

For aim 2, we sequentially recruit SzNET+ subjects until the number of subjects in either SzNET+EEG+ or SzNET+EEG-first reaches 11 subjects. We will calculate the proportions of patients with SzNET among EEG- and EEG+ patients. and use the two-proportion Z-test to test their difference.

Plans for Aim 3.

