8.4. Planned Interim Analyses

No interim analyses will be performed.

9. Sample Size Rationale

There is no preliminary data for effect size estimation using the paradigm and patient population suggested in this study. In Aim 1, a paired t-test is used to test measurement differences before and after ASM. A effect size 0.806 can be detected for a 1-sided test at a power of 80% and a Type I error at 0.05 with the total of 11 subjects before and after ASM. In Aim 4, a transformed Z-test is used to test correlation between two variables. A correlation size 0.506 can be detected for a 1-sided test at a power of 80% and a Type I error at 0.05 with the total of 22 subjects.

10. Data Capture and Database Management

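### Sections 7.8 and 8.1(iv) give conflicting rules for dropouts, and Sections 8.3 and 9 count treated patients (22 and 11) where Section 5.1 expects 20 and 10 completers

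*Combined protocol and SAP*

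**What the plan says.** **Dropouts.** Section 7.8 defines a dropout as a patient who does not meet the treatment criterion (two listed drugs for at least 72 hours) or cannot have the second scan in its window. Enrolment data and the first scan are kept for Aim 2. Then: "However, this data cannot be used for other outcomes analysis". Section 8.1(iv), under the heading for strategies common to all aims, says "We will appropriately handle drop-outs and missing data". It names imputation or other estimation methods, lists missing responses among its examples, and promises a sensitivity analysis over different missing-data mechanisms. Section 13.1.2 adds that when a participant regains capacity and declines to continue, the data gathered so far stay in the analyses.

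**Counts.** Section 5.1 says "we need a total of 20 subjects successfully to receive the study therapy AND repeat rs-fMRI" and, at 1-in-10 attrition, plans to treat 22: 11 per EEG stratum to obtain 10. On Aim 1, Section 8.3 reads "Therefore, 22 subjects with measurements before and after", meaning paired scans around treatment, and it also uses 22 for Aims 3 and 4.

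**Detectable effects.** Section 9 says of Aim 1 that "a paired t-test is used to test measurement differences before and after ASM". The figure given is "A effect size 0.806 can be detected for a 1-sided test at a power of 80% and a Type I error at 0.05". The sample size behind that figure is stated as "with the total of 11 subjects before and after ASM". For Aim 4 it says "A correlation size 0.506 can be detected for a 1-sided test", based on 22 patients and the same power and error rate.

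**The concern.** An analyst following Section 7.8 would analyse completers only for Aims 1, 3 and 4. An analyst following Section 8.1(iv) could keep treated dropouts and impute their responses. Any such imputation of volume or power-spectrum change would draw on the baseline scan, which Section 7.8 reserves for Aim 2. The analysis set for the main aims is therefore undefined, and it could be chosen after the results are seen.

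The counts carry the same ambiguity. Twenty-two patients with paired scans requires that nobody drops out, contrary to the attrition in Section 5.1. Section 9 then rests on treated patients, not on those expected to supply data. Aim 1 is meant to inform a larger placebo-controlled trial, so the analysis set and its size carry forward into that trial's planning.

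**Working it through.** **Inputs.** One-sided 5% error, 80% power, effect 0.806 at n = 11, correlation 0.506 at n = 22 (Section 9). Treated 22 and 11, completers 20 and 10, attrition 1 in 10 (Section 5.1). Aim 1 pooled across strata in an intercept-only model (Section 8.3).

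**Step 1: Aim 1, reproduce the plan.** For a paired t-test, power = P(T > t(0.95, n−1)), where T is noncentral t with n−1 degrees of freedom and noncentrality d√n. At n = 11 the critical value is 1.8125 and the noncentrality is 0.806 × √11 = 2.673, giving power 0.7999. The stated 0.806 reproduces at 11 patients.

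**Step 2: Aim 1 at other counts.**

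| n | Meaning | Detectable effect | Power at 0.806 |
|---|---|---|---|
| 11 | treated, one stratum (Section 9) | 0.806 | 80.0% |
| 10 | completers, one stratum | 0.853 | 76.0% |
| 22 | treated, pooled (Section 8.3) | 0.548 | 97.8% |
| 20 | completers, pooled | 0.577 | 96.6% |

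**Step 3: Aim 4, reproduce the plan.** Use the Fisher transform with a bias term and a t-based critical correlation: power = Φ{[atanh(r) + r/(2(n−1)) − atanh(r_c)]√(n−3)}, with r_c = t/√(t² + n − 2) and t = t(0.95, n−2). At n = 22, t = 1.7247, r_c = 0.3598 and atanh(r_c) = 0.3767. With r = 0.506, atanh(r) = 0.5573 and the bias term is 0.0120. The argument is (0.5573 + 0.0120 − 0.3767) × √19 = 0.840, so power is 79.95%. The stated 0.506 reproduces at 22 patients.

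**Step 4: Aim 4 at 20 completers.** Now t = 1.7341, atanh(r_c) = 0.3981 and the bias term is 0.0133. The argument is (0.5573 + 0.0133 − 0.3981) × √17 = 0.711, so power at 0.506 is 76.2%. The correlation detectable at 80% is 0.529. Without the bias term the detectable values are 0.516 (n = 22) and 0.539 (n = 20), and power at 0.506 is 78.4% and 74.3%.

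**Step 5: how likely are the counts?** Assume independent 10% attrition and no replacement. Expected completers are 22 × 0.9 = 19.8. The chance that all 22 complete is 0.9^22 = 9.8%; the chance that at least 20 complete is 62.0%.

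**Step 6: if enrolment stops at ten per group.** Section 5.1 also says this. Ten per cent attrition would then leave 9 per stratum and 18 pooled. Detectable effects become 0.909 (single stratum), 0.611 (pooled Aim 1) and a correlation of 0.554.

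**Step 7: size of a bounding analysis.** If 2 of 22 treated patients drop out and are scored as no change, the mean change is the completer mean × 20/22, which is 9.1% smaller.

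**The case against.** The strongest reply is that little is lost. Section 8.3 pools the strata for Aim 1, and 20 completers exceed the stated 0.806 comfortably. The 0.853 belongs to a single-stratum test that Section 8.3 does not plan; EEG status is only an optional covariate there. The Aim 4 shortfall is about four points of power in an open-label pilot that states it has no preliminary effect-size data. Section 8.1(iv) is generic and does not commit to imputing dropouts, while Section 7.8 is the specific rule. Section 5.1 may also allow replacement once Aim 2 data are complete.

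Most of this stands, and it limits the point. The replacement text does not settle the matter: it refers to reaching the strata's enrolment, not a number of completers, and it sits beside the statement that enrolment stops at ten per group. The conflict between Sections 7.8 and 8.1(iv) also remains, because 8.1(iv) names drop-outs and missing responses outright.

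A reader might infer four stronger things that the documents do not support:

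- That the primary aim is underpowered for its stated effect. The pooled test is not.
- That no sensitivity analysis is planned. Section 8.1(iv) states one; it is unspecified and would need data that Section 7.8 bars.
- That excluding dropouts inflates the response. Adverse events, or a condition that prevents the second scan, could remove poor responders. Section 13.1.2, however, lets patients who regain capacity decline further tests, which could remove good ones. The direction is not established.
- That patients scanned before 72 hours of treatment could simply be retained. Sections 4.1 and 6 allow the second scan only after that time, and Section 7.8 does not plan to collect such data.

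**Conclusion.** The dropout rules conflict and the analysed counts are wrong under the plan's own attrition. With 20 and 10 completers and no replacement, power at the stated effects is about 76% for the Aim 4 correlation and for a single-stratum Aim 1 test. The corresponding detectable values are 0.529 and 0.853. For the pooled Aim 1 test the stated 0.806 is conservative, so the fault there is that Section 9's 11 does not match Section 8.3's pooled analysis.

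The Aim 4 figures describe a correlation, whereas Section 8.3 plans logistic regression on a binary split. Neither 0.506 nor 0.529 describes that test at any sample size. The effect on power is small; the undefined analysis set is the more important defect. This should be corrected before analysis, but it does not threaten the trial.

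**What to change.** - **One dropout rule.** Make completers the primary set for Aims 1, 3 and 4, and have Sections 7.8, 8.1(iv) and 13.1.2 agree with it.
- **Counts.** Change 22 in Section 8.3 to about 20 expected, or state that dropouts are replaced until 20 or 22 complete. Reconcile the replacement sentence in Section 5.1 with its stop at ten per group.
- **Section 9.** Give Aim 1 pooled (n = 20, 0.577) and, if a per-stratum figure is wanted, n = 10, 0.853. Restate Aim 4 at n = 20 (0.529), noting that this is for a correlation and not for the planned logistic regression.
- **Sensitivity analysis.** Allow dropouts' baseline data to be used for it. Count treated dropouts as zero change in Aim 1 and as non-improvement in Aims 3 and 4, presented as a bound with no presumed direction of bias.

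The cost is protocol and SAP wording and slightly less favourable stated figures for Aim 4 and for any per-stratum claim. No extra patients are needed unless the sponsor chooses replacement.
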